expected. Thus, in order to achieve desired numbers of intervention participants, when we reached over 400 in the control group, we began assigning 100% of participants who were randomly selected to be emailed to the intervention group. Because participants were recruited via professors and fliers were not randomly selected, these participants were randomized 50/50. Thus, 65.9% of participants were assigned to the intervention ($n = 836$) and 34.1% were assigned to control ($n = 432$). Participants randomized into the intervention group were invited to attend the intervention, which was conducted in two sessions (initial session and booster session). Initial session attendance was 36.2% ($n = 303$); of those, 83.1% ($n = 252$) attended the booster.

Participants first completed the baseline survey (Time 1). An average of two weeks later, those in the intervention group participated in the first intervention session. The follow-up survey (Time 2) occurred 6 months after the first intervention session, and, for control participants, 6 months and 2 weeks after their baseline survey (to ensure receipt of email at times comparable to intervention participants). We sent participants up to eight total text, email, and call reminders to remind them of the Time 2 survey. Of the 1,268 baseline participants, 70.1% ($n = 889$) completed the Time 2 survey, including 314 in the control condition and 575 in the intervention group. Participants received \$15 and \$25 gift cards for completing Time 1 and 2, respectively. Of the 305 participants who attended the first session, 252 (82.6%) attended the booster session. Participants also received reminder texts, emails, and calls to remind them about the initial and booster sessions; they received up to five of these reminders.

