**Analysis Plan for:**

**Development and Pilot Trial of an Intervention to Reduce Disclosure Recipients Negative Social**

**Reactions and Victims Psychological Distress and Problem Drinking**

**NCT03488927**

**Last approved August 25, 2020**

**Contents:**

**Analysis Plan**

## Analysis Plan

**Main effects.** Treatment effect analyses compared participants in the intervention group who attended (Tx-Attender;  $n = 305$ ) to both: (a) participants who were invited to the treatment but who did not attend (Tx-Nonattender;  $n = 531$ ) and (b) participants in the control group ( $n = 432$ ). We conducted ANCOVA analyses in SPSS. We added contrasts to compare the three groups using the /LMATRIX subcommand. Covariates included gender, year in college, and alcohol use in the past 30 days, based on baseline differences in these variables. We used these covariates for all models except those models including alcohol use frequency or binge drinking as moderators, where we only included gender and year in college (because there was no variability in alcohol use in the past 30 days with these moderators).

Dependent variables differed by hypothesis. To test Hypothesis 1, we compared the three groups on T2 intended reactions, among participants who responded about intentions at T2 ( $n = 415$ ). To test Hypothesis 2, we compared the three groups on T2 actual reactions, among participants who responded about actual reactions at T2 ( $n = 474$ ). To test Hypothesis 3, we compared the T2 scores on intermediary variables of all participants, with the T1 score of each outcome as a covariate to assess for differences in change.

**Moderation analyses.** We explored four categories of moderators: demographic, IPV/SA, alcohol use, and characteristics of actual disclosures. To explore moderation, intervention condition was operationalized via two dummy codes: Tx-Attender (1) vs. Control (0) and Tx-Attender (1) vs. Tx-Nonattender (0). We then entered these dummy-coded variables into a regression model in SPSS along with covariates consistent to the covariates in the main effect analysis, main effect of the moderator, and the two interactions of interest (i.e., interaction between each dummy-coded treatment variable and moderator). For example, for gender, we

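### Disclosure characteristics exist for only 474 of 889 T2 responders but are modelled like baseline moderators, which can bias simple effects and, under a further condition, interactions

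*SAP*

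**What the plan says.** The SAP (Analysis Plan, Moderation analyses) names four moderator categories, "demographic, IPV/SA, alcohol use, and characteristics of actual disclosures", and gives them all one model. That model has the covariates, the moderator's own term and two products of the moderator with the group dummies. After a significant interaction, the intervention's effect is estimated at each level of a dichotomous moderator, or one SD either side of the mean for a continuous one. The only exclusion rule concerns very small groups. No rule concerns when a moderator was measured.

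The SAP (Main effects) tests Hypothesis 2 on T2 reactions "among participants who responded about actual reactions at T2", giving 474 participants. Hypothesis 1 uses the 415 who answered about intentions. The Protocol (Procedures) reports that "70.1% ($n = 889$) completed the Time 2 survey" and, on timing, that "The follow-up survey (Time 2) occurred 6 months after the first intervention session". Neither document gives the recall window for the disclosures or the survey that recorded their characteristics. Neither plans a comparison of disclosure receipt or type between groups.

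**The concern.** Demographic, IPV/SA and alcohol variables can be fixed at T1, before assignment can affect them. The features of a disclosure received during follow-up cannot. The intervention is aimed at people who receive disclosures, so it could plausibly change who confides in a participant and what is confided. Attenders may also differ in this respect without any intervention effect, because attendance was not randomised. If either happens, participants with the same kind of disclosure are not comparable across groups. Adjustment for gender, year in college and recent drinking is unlikely to remove the difference.

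What is at stake is a conclusion that the intervention works better for certain kinds of disclosure. Under some conditions that pattern could appear with no effect in anyone.

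**Working it through.** **1. Counts.** 415 + 474 = 889, exactly the number of T2 completers. This fits a split of T2 responders by whether they had a disclosure to report. The actual-reaction set is 474/889 = 53.3% of T2 responders and 474/1,268 = 37.4% of baseline participants. Disclosure characteristics can exist only in this set.

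**2. Timing.** Hypothesis 2 treats a group difference in T2 actual reactions as a treatment effect. That makes sense only if the disclosures followed the intervention. Post-assignment timing is therefore a reasonable inference, but it is not a stated fact.

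**3. Size of bias.** The documents give no inputs for this, so every setting here is an assumption. There are two groups T, a true effect and true interaction of zero, an unmeasured trait U, and independent standard normal errors e:

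- Receipt: c·T + 0.5·U + √0.75·e exceeds a threshold set so that 474/889 of untreated people receive a disclosure.
- Characteristic: M = 1 if a·T + (0.5 + h·T)·U + √0.75·e > 0.
- Reaction: Y = 0.5·U + √0.75·e.

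Y was regressed on T, M and T×M among receivers, with 2,000,000 people simulated per row. Results are in SD units; the truth is 0 in every cell.

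| a | c | h | Effect at M=0 | Effect at M=1 | Interaction |
|---|---|---|---|---|---|
| 0 | 0 | 0 | 0.006 | 0.000 | -0.006 |
| 0.3 | 0 | 0 | -0.044 | -0.039 | 0.005 |
| 0 | 0.3 | 0 | -0.044 | -0.037 | 0.007 |
| 0.3 | 0.3 | 0 | -0.084 | -0.070 | 0.014 |
| 0.5 | 0.5 | 0 | -0.145 | -0.116 | 0.029 |
| 0 | 0 | 0.4 | -0.109 | 0.050 | 0.159 |
| 0.3 | 0.3 | 0.4 | -0.204 | -0.019 | 0.186 |
| 0 | 0 | -0.4 | 0.160 | -0.106 | -0.267 |

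The first row shows simulation noise. With a = c = 0.3 but U removed from the reaction, all three results are within 0.004 of zero.

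For a continuous M and h = 0, shifts bias the effects at ±1 SD by 0.03 to 0.18, and the interaction per unit of M is at most 0.008. With h = ±0.4, the low and high effects differ by 0.10 to 0.30 in absolute value (for example 0.012 − (−0.090) = 0.102, and −0.132 − 0.172 = −0.304).

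A second simulation had no receipt step and 400,000 people per scenario. The characteristic was shifted by 0.3 to 0.5 probit units, the trait's effect on it was 0.5 to 0.7, and the trait's correlation with the outcome was 0.4 to 0.5. The effects at M=1 and M=0 were (−0.026, −0.030), (−0.054, −0.057) and (−0.069, −0.074), so the interactions were 0.004, 0.003 and 0.005. Letting the intervention change the trait's influence by 0.3 to 0.4 gave (0.022, −0.085) and (−0.003, −0.147), so the interactions were 0.107 and 0.144.

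**4. Scale against this trial's precision.** Assume equal retention across attenders and non-attenders and an equal receipt share in all groups. The attenders in the set number 575 × 305/836 × 474/889 ≈ 112, and the controls 314 × 474/889 ≈ 167. With a 50/50 binary moderator and SD 1:

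- SE(interaction) = √(4/112 + 4/167) = 0.24
- SE(simple effect) = √(2/112 + 2/167) = 0.17

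At a two-sided 5% level (assumed; the SAP states none), the false-positive rate is Φ(−1.96 − d) + Φ(−1.96 + d), with d = bias/SE. A bias of 0.03 gives about 5%, 0.11 to 0.14 gives about 7% to 9%, and 0.16 to 0.27 gives about 10% to 20%.

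**The case against.** The strongest reply is that bias is conditional. It needs an effect of the intervention or attendance on disclosure receipt or type, and also an unmeasured cause shared with the reaction. The documents report neither, and without either one the bias is about zero. That stands. A reader might infer that these models necessarily give biased simple effects and invalid interactions, but the documents do not support that. The interaction is close to unbiased under simple shifts and is materially wrong only under a third assumption.

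Three further points stand. Simple effects are probed only after a significant interaction, so the bias that arises without an interaction would seldom be reported. The gate does not correct those estimates once they are reported, however. The SAP presents moderation as exploratory, and one category of four is affected. The simulations treat the intervention as a randomised two-group exposure, whereas the plan's contrasts use self-selected attenders.

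Two replies do not remove the point. It is true that the recall window is unstated. But if some disclosures predated the first session, reactions to them could not show an intervention effect, so the timing needs stating either way. It is also true that moving to T1 moderators leaves the attender contrasts non-randomised. Correcting those contrasts would equally leave this moderator open to influence by treatment.

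**Conclusion.** The point holds in a limited form. The plan handles a variable that exists only in a subset defined at T2, and that the intervention could change, as if it were a baseline modifier, with no caution on interpretation. Simple effects are the more exposed quantity: about 0.03 to 0.15 SD for a binary characteristic under shifts of 0.3 to 0.5, against a standard error near 0.17. Interactions are off by about 0.03 SD or less under such shifts. They reach roughly 0.1 to 0.3 SD only if the intervention also changes how unmeasured factors relate to disclosure type.

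These sizes are illustrations under assumed settings, not estimates for this trial. Post-assignment timing is inferred from Hypothesis 2. A reader might also conclude that the category has to be deleted. That is more than is needed: the analysis can stay if it is read as descriptive.

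**What to change.** In the SAP's Moderation analyses:

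- State when the reported disclosures occurred and which survey recorded each moderator.
- Limit conclusions about effect modification to variables measured at T1.
- Report disclosure receipt and disclosure characteristics by assigned arm as descriptive outcomes.
- If the disclosure-characteristic models are kept, label them exploratory associations among disclosure recipients, and draw no conclusion that the intervention works better for certain disclosures.

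This needs changes of wording and a descriptive table, with no new data. The cost is that one exploratory analysis loses its causal reading. It does not repair the non-randomised attender contrasts or the selection into the Hypothesis 2 set, which need their own treatment.
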